10.0 QUALITY CONTROL AND QUALITY ASSURANCE PROCEDURES

10.1 Monitoring of the Study and Regulatory Compliance

The project manager, or designee, will make an initiation site visit to each institution to review the protocol and its requirements with the Investigator(s), inspect the drug storage area, fully inform the Investigator of his/her responsibilities and the procedures for assuring adequate and correct documentation. During the course of the study, the monitor will make regular site visits in order to review protocol compliance, examine CRFs and individual subject's medical records and assure that the study is being conducted according to pertinent regulatory requirements. All CRF entries will be verified with source documentation. The review of medical records will be done in a manner to assure that patient confidentiality is maintained.

10.2 Curricula Vitae and Financial Disclosure of Investigators

All Principal Investigators will be required to provide a current signed and dated curriculum vitae, a completed FDA Form 1572 and a financial disclosure statement to Theradex Oncology. All Sub-investigators will be required to provide a current curriculum vitae and a financial disclosure statement to Theradex Oncology.

10.3 Protocol Modifications

No modification of the protocol should be implemented without the prior written approval of the Sponsor or the Sponsor's representative (Theradex Oncology). Any such changes which may affect a patient's treatment or informed consent, especially those increasing potential risks, must receive prior approval by the IRB/IEC. The exception to this is where modifications are necessary to eliminate an immediate hazard to trial subjects, or when the change involves only logistical or administrative aspects of the trial (e.g. change in monitor, change in telephone number). Other administrative revisions which may impact the clinical portion of a study will be duly reported to the IRB/IEC by the Principal Investigator.

10.4 Publication Policy

The publication of the results of the study will be subject to the terms and conditions of the clinical trial agreement between the Sponsor and Investigators. Sponsor approval is required for publication of any data from this trial.

11.0 ETHICAL CONSIDERATIONS

11.1 Informed Consent

The Investigator will obtain written informed consent from each patient, or the patient's authorized representative, participating in the study. The form must be signed and dated. The ICF will contain all the Essential Elements of Informed Consent set forth in 21 CFR, Part 50, the European Union Directive 2001/20/EC and its associated Detailed Guidances, European Union GCP Directive 2005/28/EC, the ICH Guideline for Good Clinical Practice, Section 4.8, and the terms of the Declaration of Helsinki (2008). Copies of the signed document should be given to the patient and filed in the patient's medical record if in conformance with the institution's Standard Operating Procedures.

In cases incapacitated subjects are to be included, two sets of information sheets might be needed according to national regulations. In addition to the information given to the patient's legal representative, the patient should be given information according to his/her capacity to understand. This information should include, where appropriate, a statement that the patient's decision not to participate or to withdraw from a trial will be respected, even if consent is given by the parent/legal representative.

11.2 Institutional Review Board/Independent Ethics Committee (IRB/IEC)

The study will not be initiated without approval of the appropriate IRB/IEC and compliance with all administrative requirements of the governing body of the institution. This protocol, consent procedures, and any amendments must be approved by the IRB/IEC in compliance with current regulations of the FDA and the European Union as applicable and in accordance with ICH/GCPs. A letter of approval will be sent to the Sponsor prior to initiation of the study and when any subsequent modifications are made. The IRB/IEC will be kept informed by the Investigator, Theradex Oncology or the Sponsor, as required by national regulations, as to the progress of the study as well as to any serious and unexpected adverse events.

11.3 Patient Privacy

In order to maintain patient confidentiality, all CRFs, study reports and communications relating to the study will identify patients by initials and assigned patient numbers; patients should not be identified by name. In accordance with local, national or federal regulations, the Investigator will allow the Sponsor or designee personnel access to all pertinent medical records in order to verify the data gathered on the CRFs and to audit the data collection process. Regulatory agencies such as the US Food and Drug Administration (FDA) may also request access to all study records, including source documentation for inspection. Clinical information will not be released without the written permission of the patient as outlined in the patient consent form.

12.0 DATA HANDLING AND RECORD KEEPING

12.1 Data to be Entered Directly in the CRF

The CRF will be the source record for the following data: None

12.2 Recording of Data

Data collected during the study will be recorded in the patient's CRF by the investigational site staff. The staff will keep records of the patient's visit in the files considered as source documents for the site, e.g., hospital chart, patient medical records. The Investigator will be responsible for the recording of all data on the CRF and for submitting the data to the Sponsor or their designee in a timely manner. Should any value be significantly different from normal, the Investigator will comment in the appropriate sections provided in the CRF.

The Investigator will provide access to his/her original records to permit a representative from the Sponsor to verify the proper transcription of data. To facilitate photocopying, entries must be recorded legibly in black ink only. Erroneous entries will be crossed out with a single line, so as to remain legible. The correct value will be entered above the error and then initialed and dated by the person authorized to make the correction.

12.3 Study Records

U.S. Federal laws require that an Investigator maintain all study records for the indication under investigation for two years following the date a Product Licensing Application is approved or, if no application is to be filed or if the application is not approved for such indication, until two years after the investigation is discontinued and the FDA is notified.

APPENDIX I – ECOG PERFORMANCE STATUS

Grade

- | | |
|---|--|
| 0 | Fully active, able to carry on all pre-disease performance without restriction. |
| 1 | Restricted in physically strenuous activity but ambulatory and able to carry out work of a light or sedentary nature, e.g., light house work, office work. |
| 2 | Ambulatory and capable of all self-care but unable to carry out any work activities. Up and about more than 50% of waking hours. |
| 3 | Capable of only limited self-care, confined to bed or chair more than 50% of waking hours. |
| 4 | Completely disabled. Cannot carry on any self-care. Totally confined to bed or chair. |
| 5 | Dead. |

**APPENDIX II – PROPOSED MODIFIED INTERNATIONAL WORKING GROUP
 RESPONSE CRITERIA FOR ALTERING NATURAL HISTORY OF MDS**

(from Cheson et al, Blood 2006)

Category	Definition
Complete remission (CR)	Bone marrow blasts $\leq 5\%$ myeloblasts with normal maturation of all cell lines* Persistent dysplasia will be noted* [‡] Peripheral blood \diamond Hemoglobin (Hgb) ≥ 11 g/dL Platelets $\geq 100 \times 10^9/L$ Neutrophils $\geq 1.0 \times 10^9/L$ \ddagger Blasts 0%
Partial remission (PR)	All CR criteria if abnormal before treatment except: Bone marrow blasts decreased by $\geq 50\%$ over pretreatment but still $> 5\%$ Cellularity and morphology not relevant
Marrow CR \neq	Bone marrow: $\leq 5\%$, myeloblasts and decrease by $\geq 50\%$ over pretreatment \ddagger Peripheral blood: if HI responses, they will be noted in addition to marrow CR \ddagger
Stable disease	Failure to achieve at least PR $<$ but no evidence of progression for > 8 weeks
Failure	Death during treatment or disease progression characterized by worsening of cytopenias, increase in percentage of bone marrow blasts, or progression to a more advanced MDS FAB subtype than pretreatment
Relapse after CR or PR	At least 1 of the following: Return to pretreatment bone marrow blast percentage Decrement of $\geq 50\%$ from maximum remission/response levels in granulocytes or platelets Reduction in Hgb concentration by ≥ 15

	g/dL or transfusion dependence
Cytogenic response	Complete = Disappearance of the chromosomal abnormality without appearance of new ones Partial = at least 50% reduction of the chromosomal abnormality
Disease progression	For patients with: Less than 5% blasts: $\geq 50\%$ increase in blasts to $> 5\%$ blasts; 5-10% blasts: $\geq 50\%$ increase to $> 10\%$ blasts; 10-20% blasts: $\geq 50\%$ increase to $> 20\%$ blasts; 20-30% blasts: $\geq 50\%$ increase to $> 30\%$ blasts Any of the following: At least 50% decrement from maximum remission/response in granulocytes or platelets Reduction in Hgb by ≥ 2 g/dL Transfusion dependence
Survival	Endpoints: Overall: death from any cause Event free failure or death from any cause PFS: disease progression or death from MDS DFS: time to relapse Cause-specific death: death related to MDS

Deletions to IWG response criteria are not shown.

To convert hemoglobin from grams per deciliter to grams per liter, multiply grams per deciliter by 10.

* Dysplastic changes should consider the normal ranges of dysplastic changes (modification) ³⁵

* Modification to IWG response criteria.

◊ In some circumstances, protocol therapy may require the initiation of further treatment (eg, consolidation, maintenance) before the 4-week period. Such patients can be included in the response category into which they fit at the time the therapy is started. Transient cytopenias during repeated chemotherapy courses should not be considered as interrupting durability of response, as long as they recover to the improved counts of the previous course.

Proposed modified IWG response criteria for hematologic improvement

Hematologic improvement	Response criteria (responses must last at least 8 weeks) [†]
Erythroid response (pretreatment, < 11 g/dL)	Hgb increase by ≥ 1.5 g/dL Relevant reduction of units of RBC transfusions by an absolute number of at least 4 RBC transfusions/8 weeks compared with the pretreatment transfusion number in the previous 8 wk. Only RBC transfusions given for a Hgb of ≤ 9.0 g/dL pretreatment will count in the RBD transfusion response evaluation [†]
Platelet response (pretreatment, < $100 \times 10^9/L$)	Absolute increase of $\geq 30 \times 10^9/L$ for patients starting with $> 20 \times 10^9/L$ and by at least 100% [†]
Neutrophil response (pretreatment, < $1.0 \times 10^9/L$)	At least 100% increase and an absolute increase $> 0.5 \times 10^9/L$ [†]
Progression or relapse after HI [‡]	At least 1 of the following: At least 50% decrement from maximum response levels in granulocytes or platelets Reduction in Hgb by ≥ 1.5 g/dL Transfusion dependence

Deletions to the IWG response criteria are not shown.

To convert hemoglobin levels from grams per deciliter to grams per liter, multiply grams per deciliter by 10.

Hgb indicates hemoglobin; RBC: red blood cell; HI: hematologic improvement.

*Pretreatment counts averages of at least 2 measurements (not influenced by transfusions) 1 week apart (modification). ³⁵

[†]Modification to IWG response criteria.

‡In the absence of another explanation, such as acute infection, repeated courses of chemotherapy (modification), gastrointestinal bleeding, hemolysis, and so forth. It is recommended that the 2 kinds of erythroid and platelet responses be reported overall as well as by the individual response pattern.

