7.6 Long-Term Follow-Up

This can be done remotely (e.g. via telephone, via General Practitioner or via review of medical records).

Assuming there is no withdrawal of consent, patients who stop study treatment (APR-246 or azacitidine) for any reason (e.g. toxicity, transition to SCT, PD) will continue long-term follow-up:

1. Patients who discontinue study treatment to receive SCT:
 - a. Collect post SCT response assessments, transformation to AML and survival every month until relapse or death, whichever occurs first.
 - b. After PD, collect data for survival and transformation to AML every 6 months until death.
2. Responders (CR, PR, mCR with HI, mCR without HI, HI) who discontinue study treatment for other reasons than progressive disease or SCT:
 - a. Collect response assessments, transformation to AML and survival monthly until relapse or death, whichever occurs first.

- b. After relapse/progression, continue collecting data for survival and transformation to AML every 6 months until death.
3. Non-Responders: patients who discontinue study treatment due to progressive disease:
 - a. Collect data for survival and transformation to AML every 6 months until death.

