8.2.3 Stem Cell Transplant

Patients may go on to receive SCT and this is likely to be a reflection of a positive outcome to treatment with the randomized therapies. The primary approach will be to use a treatment policy strategy (ICH E9 (R1) addendum)³³ where patients who receive SCT will continue to be followed for OS and relapse from any response with their date of death/relapse used in the analysis. If for any reason a patient receives SCT prior to a documented CR they will not be counted as a response. The inverse probability of censoring weights (IPCW)³⁴ method will be used adjusting for baseline predictors of outcome and time-dependent covariates such as blast, platelet and neutrophil counts. For patients who receive SCT, this method effectively replaces their outcome with patients who most resemble them and who do not receive SCT, in terms of response treatment and baseline attributes. The IPCW approach is preferred to censoring patients who receive SCT, as receipt of SCT is associated with a good response to therapy and would introduce informative censoring and underestimate the true DOR.

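### Relapse after transplant is judged by general count and transfusion criteria with no exemption for SCT, so transplant cytopenia can be dated as the end of CR

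*Combined protocol and SAP*

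**What the plan says.** Duration of CR is part of the primary objective (section 3.1) and of the primary endpoint (section 8.2). Section 9.3.1 ends DOR at relapse, progression or death from any cause, and summarises duration of CR in each arm by a Kaplan-Meier median with its 95% CI.

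Section 8.2.3 makes treatment policy the primary approach to SCT: "patients who receive SCT will continue to be followed for OS and relapse from any response with their date of death/relapse used in the analysis". It also plans an inverse probability of censoring weights (IPCW) analysis, with blast, platelet and neutrophil counts among the time-dependent covariates.

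For patients who stop treatment to receive SCT, section 7.6 says: "Collect post SCT response assessments, transformation to AML and survival every month until relapse or death, whichever occurs first". On the mode of follow-up it says: "This can be done remotely (e.g. via telephone, via General Practitioner or via review of medical records".

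Appendix II holds the only relapse criteria, and any one limb suffices:
- **Relapse after CR or PR** includes a fall of at least 50% "from maximum remission/response levels in granulocytes or platelets". A further limb ends "g/dL or transfusion dependence".
- **Disease progression** repeats the count limb, "At least 50% decrement from maximum remission/response in granulocytes or platelets", and also lists transfusion dependence.

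Two footnotes soften the criteria. The note to the main response table says: "Transient cytopenias during repeated chemotherapy courses should not be considered as interrupting durability of response", provided that counts recover to those of the preceding course. A second note, which asks that no other explanation be present, is marked on the row for progression or relapse after hematologic improvement (HI).

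**The concern.** A patient who goes to transplant in CR has, by the CR definition, platelets of at least 100 and neutrophils of at least 1.0 (× 10⁹/L). Conditioning and the wait for engraftment can push counts below half of the best response and can require transfusion, with no return of disease. The count and transfusion limbs carry no cause, so on their wording such a patient can qualify as relapsed. Treatment policy then uses that date.

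The error need not be equal between arms. SCT is offered after a response, and section 8.2.3 itself regards SCT as likely to reflect a good outcome. More transplants may therefore occur in the arm that works better, and false relapses would gather there. A strategy chosen so that transplant would not distort duration would then be undermined by the event definition. Few patients carry this estimate, so a handful of misdated events could be visible.

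**Working it through.** **1. The plan's own figure.** Section 9.1 gives 77 per arm for 50% v 25%, 90% power, two-sided alpha 0.05. With pooled variance:

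n = [1.96·√(2·0.375·0.625) + 1.2816·√(0.5·0.5 + 0.25·0.75)]² / 0.25² = (1.342 + 0.848)² / 0.0625 ≈ 76.7, so 77 per arm. Power at 77 is 90.1%.

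The figure reproduces, and the present point does not touch it. CR is scored before SCT, and section 8.2.3 does not count SCT before a documented CR as a response.

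**2. Patients who inform duration of CR.** 77 × 0.50 = 38.5 and 77 × 0.25 = 19.25 expected CRs.

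**3. Do the footnotes cover SCT?** The main-table note speaks of repeated chemotherapy courses and recovery to the previous course's counts. SCT patients are removed from study treatment (section 4.1). The other note is marked on the HI row, not on relapse after CR or PR. Neither names SCT, and no engraftment window is given elsewhere.

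**4. Illustration of size.** The documents give no SCT rate, SCT timing or post-SCT counts. Inputs:
- median response duration m = 7 months: Table 1 footnote, TP53-mutated patients in the study where all received azacitidine (any response, used here for CR);
- *assumed:* share f of CR patients for whom SCT is planned, 40% v 10%;
- *assumed:* SCT at s months after CR if still in CR, with s = 3 to 6;
- *assumed:* post-SCT median remission of 14 months, with 7 as the alternative;
- *assumed:* share q of SCTs scored as relapse one month after SCT.

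S(t) = (1 − f)·2^(−t/7) + f·G(t), where G(t) = 2^(−t/7) before s and 2^(−s/7)·2^(−(t−s)/14) from s on, multiplied by (1 − q) from s + 1. The median solves S(t) = 0.5.

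Checks at s = 3:
- f = 0.4, q = 0, t = 8.1: 0.6·0.448 + 0.4·0.743·0.777 = 0.500, so the median is 8.1.
- f = 0.4, q = 1: S is 0.687 just before month 4 and 0.6·0.673 = 0.404 just after, so the median is 4.0.
- f = 0.1, q = 1: 0.9·2^(−t/7) = 0.5, so t = 7·log₂(1.8) = 5.9.

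Median duration of CR in months, 40% v 10% planned for SCT, post-SCT median 14:

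| SCT at | q = 0 (true) | q = 25% | q = 50% | q = 100% |
|---|---|---|---|---|
| 3 months | 8.1 v 7.2 | 6.6 v 6.9 | 5.0 v 6.6 | 4.0 v 5.9 |
| 4 months | 7.8 v 7.2 | 6.3 v 6.9 | 5.0 v 6.6 | 5.0 v 5.9 |
| 5 months | 7.5 v 7.1 | 6.1 v 6.8 | 6.0 v 6.5 | 6.0 v 6.0 |
| 6 months | 7.3 v 7.1 | 7.0 v 7.0 | 7.0 v 7.0 | 7.0 v 7.0 |

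With a post-SCT median of 7 and SCT at 3 months, the true medians are equal at 7.0. They read 5.9 v 6.7 at q = 25% and 4.0 v 5.9 at q = 100%.

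The round values (4.0, 5.0, 6.0, 7.0) arise because the model puts all misscored events on one day, s + 1. At s = 6 the medians hardly move, but the false events still lower the curve from month 7.

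**The case against.** The other side has several fair points.

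- **Nothing shows that misscoring must happen.** The documents give no post-SCT counts and no post-SCT blood-count schedule, and follow-up may be remote. A reader might infer that CR necessarily ends at the first monthly assessment after SCT. The documents support only that it can. This stands.
- **An assessor could stretch the footnotes.** The main-table note also mentions further treatment such as consolidation, and its principle could be extended to transplant. The marker on the HI row sits in a table that came through text extraction damaged. This stands in part: a sensible assessor may do so, but the wording does not require it, and in an open-label multicentre trial that leaves the event to local judgement.
- **IPCW is planned.** It describes the outcome had SCT not been given, so post-SCT count falls should not drive it. But section 8.2.3 names treatment policy as primary, and IPCW leaves that estimate as it is.
- **The error may be recoverable.** A reader might infer that a false relapse could never be corrected because follow-up then thins out. For SCT patients section 7.6 moves to six-monthly contact after PD. Survival and AML transformation are still collected, and CRF entries are checked against source. Irrecoverability is not established.
- **The consequence is limited.** Power and the CMH test concern the CR rate. For duration of CR, section 9.3.1 gives medians and CIs by arm, with no between-arm test or alpha. This stands.
- **A 14-month post-SCT median is generous,** since section 2.2 reports that TP53 mutation predicts lack of benefit from allogeneic transplant. With 7 months there is no true advantage to reverse, although a spurious difference still appears.

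**Conclusion.** The point holds as a defect in the event definition. Appendix II as written can date transplant cytopenia or transfusion as relapse, and the primary SCT strategy then uses that date. The effect on duration of CR, DOR and RFS would be larger in the arm that transplants more.

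Its size is unknown. Under the stated assumptions, a true 8.1 v 7.2 months reads 6.6 v 6.9 with a quarter of SCTs misscored and 4.0 v 5.9 with all misscored. With SCT at 6 months both arms read about 7.0. A reader might infer that the plan will reverse the duration result. The documents do not support that, because it depends on early SCT, unequal SCT rates, longer remission after SCT and the share misscored, none of which they give. Nor is the CR comparison at risk.

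The printed haemoglobin threshold for relapse (15 g/dL) may have lost a decimal point and plays no part here. The change should be made because it is small and concerns a component of the primary objective.

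**What to change.** In Appendix II and section 8.2.3, add an endpoint rule for the period after SCT:
- Falls in counts and transfusions attributable to conditioning, engraftment or transplant complications are not relapse or progression for the endpoint.
- Post-SCT relapse is dated from documented disease recurrence: return of marrow or blood blasts, or other documented recurrence of MDS or AML.
- The CRF records the basis of each relapse (blasts, counts, transfusion, other).
- Monthly collection under section 7.6 continues until that event or death.
- The rule applies identically in both arms.

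This is a scoring rule and alters no patient's treatment. It costs about two sentences and one CRF field. The downside is that a true relapse that first shows as cytopenia after SCT is dated slightly later, when recurrence is documented. The CRF field allows a sensitivity analysis under the literal criteria.

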APPENDIX III – NEW YORK HEART ASSOCIATION (NYHA) CLASSIFICATION

NYHA grading		MET*
Class I	No limitations. Ordinary physical activity does not cause undue fatigue, dyspnea or palpitations (asymptomatic LV dysfunction)	>7
Class II	Slight limitation of physical activity. Ordinary physical activity results in fatigue, palpitation, dyspnea or angina pectoris (mild CHF).	5
Class III	Marked limitation of physical activity. Less than ordinary physical activity leads to symptoms (moderate CHF)	2 – 3
Class IV	Unable to carry on any physical activity without discomfort. Symptoms of CHF present at rest (severe CHF).	1.6

*MET (metabolic equivalent) is defined as the resting VO₂ for a 40-year-old 70kg man. 1 MET = 3.5mL O₂/min/kg body weight.

